2.2.4 Immunogenicity analysis set

The immunogenicity (IG) set includes two parts: IG prevalence set and IG incidence set:

- The IG prevalence set includes all patients in the Safety set with a non-missing baseline ADA sample or at least one non-missing post-baseline ADA sample.
- The IG incidence set includes all patients in the Immunogenicity prevalence set with a non-missing baseline ADA sample and at least one non-missing post-baseline ADA sample.

Note that the two datasets are specific to a study drug (in this study, only PDR001) with ADA sample drawn to detect monoclonal antibodies specific to that drug.

2.2.5 PK/ECG Analysis Set

The PK/ECG analysis set includes all patients who provide baseline ECG data and at least one post-dose matched PK-ECG record (as defined in [Section 5.6](#)). Any PK-ECG analyses will be based on the PK/ECG analysis set.

2.2.6 Patient Classification

Patients may be excluded from the analysis populations defined above based on the protocol deviations (PD) entered in the database and/or on specific patient classification rules defined in [Table 2-2](#).

Table 2-2 Patient classification based on PDs and non-PD criteria

Analysis set	Protocol deviations leading to exclusion	Non protocol deviation leading to exclusion
Full analysis set	No written informed consent Mis-randomized patients as defined in Section 2.2.1	Patients who did not receive at least one dose of NIR178 or PDR001
Safety set	No written inform consent	Patient who did not receive at least one dose of NIR178 or PDR001 or did not have at least one valid post-baseline safety assessment.
PK Analysis Set	See definition of PK set	Patient who did not have at least one evaluable PK data for NIR178 or PDR001
IG Prevalence Set	No written informed consent	Patient did not have a non-missing baseline IG sample or at least one non-missing post-baseline IG sample
IG Incidence Set	No written informed consent	Patient did not have a non-missing baseline IG sample and at least one non-missing post-baseline IG sample
PK/ECG analysis set	See definition of PK/ECG set	Patient who did not have at least one post-dose matched PK-ECG record

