10.1 Analysis sets

10.1.1 Full Analysis Set

For Part 1, Part 3 and Japanese safety run-in part of the study, the Full Analysis Set (FAS) comprises all patients who received at least one full or partial dose of assigned combination of study drugs. Patients will be analyzed according to the planned treatment.

For Part 2 of the study: the Full Analysis Set (FAS) comprises all patients to whom study treatment has been assigned by randomization. According to the intent to treat principle, patients will be analyzed according to the treatment they have been assigned to during the randomization procedure.

The FAS will be used for all listings of raw data. Unless otherwise specified, the FAS will be the default analysis set used for all analyses.

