2.2.1 Full analysis set

For the Phase II - Part 1 and Part 3 and for the Japanese safety run-in study, the Full Analysis Set (FAS) comprises all patients who received at least one full or partial dose of assigned combination of study drugs. Patients will be analyzed according to the planned, which is the assigned treatment.

For Part 2 of the study, the FAS comprises all patients randomized to a study treatment, which in this case is treatment dosing schedule. According to the intent to treat (ITT) principle, patients will be analyzed according to the treatment they have been assigned to during the randomization procedure.

Unless otherwise specified, misrandomized patients (misrandomized in the interactive response technology (IRT) system) will be excluded from the full analysis set. Misrandomized patients include patients who are screen-failures, but have been randomized by the investigator before eligibility was finally assessed, however have not been treated. If patients were re-screened and successfully randomized, they will be included in the randomized set according to the dosing schedule treatment assigned in the last randomization.

The FAS will be used for all listings of raw data. Unless otherwise specified, the FAS will be the default analysis set used for all analyses.

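### SAP Table 2-2 conflicts with the intent-to-treat Full Analysis Set for randomised Part 2, because it excludes patients who were never dosed

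*SAP*

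**What the plan says.** **Definitions.** For Part 2, Protocol 10.1.1 states that "the Full Analysis Set (FAS) comprises all patients to whom study treatment has been assigned by randomization". SAP 2.2.1 agrees: "For Part 2 of the study, the FAS comprises all patients randomized to a study treatment". It continues: "According to the intent to treat (ITT) principle, patients will be analyzed according to the treatment they have been assigned to". Neither text sets a dosing condition for Part 2. The one carve-out in SAP 2.2.1 is for misrandomised patients, that is, screen failures who "have been randomized by the investigator before eligibility was finally assessed, however have not been treated". For Part 1, Part 3 and the Japanese run-in the FAS is different: it "comprises all patients who received at least one full or partial dose of assigned combination of study drugs".

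**Classification table.** SAP 2.2.6 opens: "Patients may be excluded from the analysis populations defined above based on the protocol deviations (PD) entered in the database". It adds that the rules in Table 2-2 may also lead to exclusion. In the FAS row, misrandomisation appears in the protocol-deviation column. The non-deviation column lists "Patients who did not receive at least one dose of NIR178 or PDR001". The row names no part.

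**Screen failures.** The introduction to Protocol Section 10, SAP 2.1 and SAP 2.2 all class as a screen failure anyone who consented and then, whatever the reason, did not begin treatment. Such patients' data are listed separately and kept out of the analyses. None of the three places makes an exception for a randomised patient.

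**Related rules.** The FAS is the default set for all analyses. SAP 2.3.1 plans a disposition count of patients randomised but not treated. SAP 2.5.3 keeps solid-tumour patients with an unknown or unassessed best response in the denominator as non-responders. SAP Section 4, on changes from the protocol, mentions only study closure and the Part 3 dose.

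**The concern.** Part 2 contains the only randomised comparison in the study, and its primary endpoint is the response rate (ORR) by NIR178 schedule. Under intent to treat, a patient randomised but never dosed stays in the denominator as a non-responder. Under Table 2-2 or the screen-failure rule, that patient disappears.

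If the exclusions were followed, the analysis would be conditioned on something that happens after randomisation. ORR would rise in any schedule with at least one responder that lost untreated patients. Unequal losses would also shift the posterior probabilities that one schedule is better than another, which SAP 2.5.2.2 says will be reported. Programmers may well build analysis-set flags from a classification table, so the row could take effect without anyone having decided to leave intent to treat.

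**Working it through.** **1. Which texts include the patient?** Take a Part 2 patient who consented, was eligible, was randomised and was never dosed.

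| Text | In the Part 2 FAS? |
|---|---|
| Protocol 10.1.1, Part 2 definition | Yes |
| SAP 2.2.1, Part 2 definition | Yes |
| SAP 2.2.1, misrandomised carve-out | Does not apply, because the patient was eligible |
| SAP Table 2-2, FAS row, non-deviation column | No |
| Screen-failure wording (Protocol 10, SAP 2.1 and 2.2) | No |

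The texts cannot be read together. If every undosed patient were already out of the FAS, the narrower misrandomised exclusion would do nothing, since it too covers only untreated patients. The Safety Set (SAP 2.2.2) is the part of the FAS that was dosed. In Part 2 that differs from the FAS only if the FAS can hold undosed patients. In Part 1, Part 3 and the Japanese run-in the FAS already requires dosing, so the conflict is confined to Part 2.

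**2. The plan's own figure.** SAP Table 3-1 uses a Beta(1/3, 1) prior with N = 20. With r responders the posterior is Beta(1/3 + r, 1 + N − r). For r = 5 the mean is (1/3 + 5)/(1/3 + 1 + 20) = 5.333/21.333 = 0.250.

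| r = 5, N = 20 | Mean (90% interval) | P(ORR < 20%) | P(20% to 33%) | P(ORR ≥ 33%) |
|---|---|---|---|---|
| SAP Table 3-1 | 0.250 (0.115, 0.414) | 0.316 | 0.498 | 0.185 |
| Recomputed | 0.250 (0.114, 0.414) | 0.319 | 0.491 | 0.190 |

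The row reproduces to within 0.01. Table 3-1 takes N = 20 as given, so no planned figure changes.

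**3. Illustration of the effect.** Assume 20 treated patients and 5 responders in a schedule, plus k patients randomised but untreated. The documents do not give k; the range 1 to 3 is an assumption. Excluding the k patients gives ORR = 5/20 = 25.0%. Keeping them as non-responders gives 5/(20 + k). The last column puts the k patients in Schedule 2 only, with 5 responders among 20 treated in each of Schedules 1 and 2 (2,000,000 posterior draws).

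| k | ORR, all randomised | Rise if excluded (points) | P(ORR ≥ 33%) | P(ORR < 20%) | P(S1 > S2) |
|---|---|---|---|---|---|
| Excluded, or none | 25.0% | – | 0.190 | 0.319 | 0.500 |
| 1 | 5/21 = 23.8% | 1.2 | 0.155 | 0.361 | 0.534 |
| 2 | 5/22 = 22.7% | 2.3 | 0.125 | 0.403 | 0.566 |
| 3 | 5/23 = 21.7% | 3.3 | 0.100 | 0.445 | 0.597 |

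**4. What the counts suggest.** The study status under Amendment 05 gives 62 Part 2 patients enrolled, 22/20/20 by schedule. The status under Amendment 06 gives 62 treated, again 22/20/20, with Part 2 closed to enrolment. The number randomised is not stated separately.

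**The case against.** A reader might infer that Table 2-2 overrides intent to treat in every part and so makes the Part 2 result a treated-only one. The documents do not support that. The lead-in to the table is permissive, and nothing ranks the table above the definitions. SAP 2.2.1 and Protocol 10.1.1 give the specific Part 2 rule, and SAP 2.2.1 names the principle behind it. In the other parts the row removes nobody whom the definition would keep.

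A reader might also infer that the reported Part 2 response rates are biased. The counts point the other way. A schedule is assigned only by randomisation, so an enrolled total split by schedule is naturally a count at or after randomisation, and it equals the treated total in each arm. This is good evidence but not proof, because the Amendment 05 status may use enrolment loosely to mean treated.

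The decision consequence is also small. Part 2 has no success threshold. The schedule was to be chosen on safety, tolerability and PK as well as response. The continuous schedule had been selected by Amendment 6, and the study has since closed for insufficient efficacy.

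Finally, the table agrees with the protocol's own screen-failure wording, so this is not purely a departure by the SAP. All of this limits the size of the point. It does not remove the contradiction over who is in the Part 2 FAS.

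**Conclusion.** The point stands as an unresolved conflict, limited to Part 2 and minor in weight. Two definitions put an eligible, randomised, undosed patient in the FAS. The Table 2-2 row and the screen-failure wording take that patient out. SAP Section 4 does not declare a treated-only set.

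If the exclusions were applied to a schedule with 20 treated patients, 5 responders and 1 to 3 untreated, ORR would be overstated by 1.2 to 3.3 percentage points and P(ORR ≥ 33%) by about 0.035 to 0.090. A schedule without responders would show no change in observed ORR. These figures rest on assumed numbers of responders and untreated patients, and on counting the untreated as non-responders. The actual effect is probably nil, but this cannot be confirmed without the number randomised.

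**What to change.** 1. In the FAS row of SAP Table 2-2, limit the no-dose exclusion to Part 1, Part 3 and the Japanese run-in. For Part 2, keep only the exclusions for missing consent and misrandomisation.
2. In SAP 2.1 and 2.2, except eligible randomised Part 2 patients from the screen-failure exclusion, and state that the matching sentence in Protocol Section 10 is read the same way. Editing the table alone would leave these patients excluded.
3. In SAP 2.5.3, say that Part 2 patients randomised but never dosed count as non-responders in the ORR denominator.
4. If a treated-only Part 2 set is intended, declare it in SAP Section 4 as a change from the protocol instead.

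The cost is a few sentences of SAP text, with no new data or method. The disposition summary in SAP 2.3.1 already supplies the number affected. If it is zero, no Part 2 result changes and the report can say so.

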7.2.2 Safety and tolerability assessments

Safety will be monitored by assessing physical examination, vital signs, body weight, performance status, hematology, chemistry, coagulation, thyroid function, pregnancy, ECG, as well as collecting of the adverse events at every visit. For details on AE collection and reporting, refer to [Section 8](#).

During the COVID-19 pandemic that limits or prevents on-site study visits, regular phone or virtual calls will occur (every 4 weeks or more frequently if needed) for safety monitoring and discussion of the patient's health status until the patient can again visit the site.

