2.2.2 Safety set

The Safety Set includes all patients from the FAS who have received at least one dose of NIR178 or PDR001. Patients will be classified according to treatment received, where treatment received is defined as:

1. The treatment assigned if it was received at least once, or
2. The first treatment received when starting therapy with study treatment if the assigned treatment was never received.

The safety set will be used for the safety summary of the study.

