2.6.2 Safety objectives

All safety analyses will be based on the safety set (see [Section 2.2.2](#)), which will be used for presenting summaries and listings by treatment groups and overall patients following the general analysis conventions defined under [Section 2.1](#).

The assessment of safety is based on the type and frequency of AEs as well as on the number of laboratory values that fall outside of pre-determined ranges (CTCAE grading limits or normal ranges as appropriate). Other safety data include electrocardiogram and vital signs.

All safety reporting will be based on observation periods defined in [Section 2.1.1.5](#).

Safety summaries (tables, figures) will primarily be based on all data from the on-treatment period with the exception of baseline data which will also be summarized where appropriate (e.g. change from baseline summaries). In addition, a separate summary for death including on treatment and post treatment deaths will be provided. Following the last administration of study treatment, adverse events (including serious adverse events), and new antineoplastic therapies will be collected for a period of 150 days. Following start of new antineoplastic therapy only treatment related adverse events will be collected. Select summaries of related adverse events will be produced for the combined on-treatment and post-treatment periods (see Protocol Section 10.5.2.2).

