2.6.2.3 Deaths

Separate summaries for on-treatment and post-treatment deaths will be produced by SOC and PT.

All deaths will be listed and post-treatment deaths will be flagged. A separate listing of deaths prior to the treatment initiation will be provided for all screened patients.

Note: “Study indication” as primary reason of death should be coded using MedDRA terms based on the diagnosis eCRF field at start of study. If not coded accordingly in the database, it still must be included in the summary table. Coded reasons for deaths will then be summarized by category ‘Study indication’ and ‘Other’ (as selected by the investigator).

The death summaries cover patients from the safety set. The count of deaths reported in safety analyses may differ from that reported in the efficacy analyses.

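### SAP Table 2-2 adds an undefined post-baseline assessment condition to the Safety Set that contradicts the exposure-only definition in SAP 2.2.2 and Protocol 10.1.2

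*SAP*

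**What the plan says.** SAP 2.2.2 states: "The Safety Set includes all patients from the FAS who have received at least one dose of NIR178 or PDR001". Protocol 10.1.2 says the same. Neither asks for any assessment after dosing.

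SAP 2.2.6 then says that "Patients may be excluded from the analysis populations defined above" on the basis of protocol deviations or the rules in Table 2-2. In the Safety set row, the column for exclusions not based on a protocol deviation reads: "Patient who did not receive at least one dose of NIR178 or PDR001 or did not have at least one valid post-baseline safety assessment".

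The set is used widely. SAP 2.6.2 states "All safety analyses will be based on the safety set", with a cross-reference to section 2.2.2, and SAP 2.6.2.3 states "The death summaries cover patients from the safety set". Exposure and dose intensity (SAP 2.4.1), concomitant therapy (2.4.2), tolerability (2.6.2.6.3) and the immunogenicity prevalence set (2.2.4) also rest on it.

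Listings are wider than summaries. SAP 2.6.2.3 says "All deaths will be listed and post-treatment deaths will be flagged", SAP 2.6.2.1 lists every adverse event on the eCRF page, and SAP 2.2.1 says "The FAS will be used for all listings of raw data".

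**The concern.** A programmer working from SAP 2.2.2 and one working from Table 2-2 can build different Safety Sets from the same data. The permissive wording in 2.2.6 does not settle which rule governs. It leaves the choice open in an open-label study that has no independent data monitoring committee (Protocol 6.4.3 and 8.6).

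The added condition also depends on what happens after dosing. A safety population is normally fixed by exposure so that no post-dose event, or absence of follow-up, can decide who is counted. Under Table 2-2 a treated patient with no qualifying post-dose record leaves both the numerator and the denominator of the safety summaries. If that patient died shortly after the first dose, the death would be missing from the on-treatment death table.

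**Working it through.** The plan states no figure to reproduce, so the check compares texts and then works out the direction of any effect.

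**1. The rules side by side**

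| Source | Condition for the Safety Set |
|---|---|
| Protocol 10.1.2 | In the full analysis set and at least one dose of either drug |
| SAP 2.2.2 | Same |
| SAP Table 2-2 | At least one dose **and** at least one valid safety assessment after baseline |

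SAP section 4 records the study's closure, the single Part 3 indication and dose level, and the dropping of the Part 3 dose-increment evaluation. It does not mention the Safety Set.

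**2. Is the added term defined?** No. Neither document says what makes a safety assessment valid, or whether an adverse event or death record is one. Protocol 7.2.2 gives a partial guide: "Safety will be monitored by assessing physical examination, vital signs, body weight, performance status, hematology, chemistry, coagulation, thyroid function, pregnancy, ECG", and the sentence goes on to include adverse event collection at each visit.

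**3. Who could be caught?**
- Protocol Table 7-7 schedules a triplicate ECG two hours after the NIR178 dose on Cycle 1 Day 1. A patient with that tracing should pass.
- Other Day 1 data help less. Vital signs are taken before infusion (Protocol 7.2.2.2). SAP 2.1.1.4 treats the last assessment on or before the treatment start date as baseline unless times are captured, so untimed Day 1 results fall into baseline.
- After Day 1, the next scheduled vital signs, hematology and chemistry are on Cycle 1 Day 15 (Protocol Tables 7-1 to 7-3).

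The exposed patient is therefore one who was dosed, has no usable post-dose ECG, leaves or dies before a later assessment, and has no adverse event or death record that is accepted as an assessment.

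**4. Direction of effect when one patient is excluded**

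Let a group have n treated patients, of whom x have the event.
- The excluded patient had the event: x/n becomes (x−1)/(n−1). This is lower whenever x < n, because n(x−1) < x(n−1) reduces to x < n.
- The excluded patient had no recorded event: x/n becomes x/(n−1). This is higher whenever x > 0.

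Applied to the possible readings of the term:

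| Reading | Adverse event rates | On-treatment death rate |
|---|---|---|
| Adverse event and death records both count | Can only rise | Recorded deaths kept; can only rise |
| Adverse event records count, a death record alone does not | Can only rise | Falls if the excluded patient died |
| Neither counts | Can fall or rise | Falls if the excluded patient died |

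The table shows the effect of removing one patient in a group with at least one event and at least one non-event.

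**The case against.** The strongest reply is that the clause has little or no practical effect.

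- SAP 2.6.2 points to the dose-only definition in 2.2.2, not to Table 2-2, and 2.2.6 is worded permissively.
- The Day 1 post-dose ECG covers most early departures. The protocol also provides for an end-of-treatment visit (7.1.3), a final evaluation at withdrawal of consent (7.1.4) and safety contacts at 30, 90 and 150 days, by telephone if needed (7.1.5).
- Deaths and adverse events remain visible in listings. An early death still counts in overall survival, because the full analysis set is the default.

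Most of this stands, and it limits the effect. It does not remove the conflict. A cross-reference to 2.2.2 does not cancel an explicit exclusion row four subsections later. A listing does not correct a summary rate: the two would simply disagree, and SAP 2.6.2.3 already allows safety and efficacy death counts to differ, so the discrepancy might pass unnoticed.

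A reader might infer more: that Table 2-2 does remove early deaths and drop-outs, or severe infusion reactions, and so biases adverse event rates downward. The documents do not support that. Protocol Table 6-2 requires vital signs about every 15 minutes during a Grade 3 or 4 infusion reaction, so such a patient would have assessments after dosing. If adverse event records count as assessments, the patients excluded have no recorded event and the rates would rise.

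**Conclusion.** The textual conflict is certain: Table 2-2 imposes a condition that SAP 2.2.2 and Protocol 10.1.2 do not contain, leaves its key term undefined, and is not declared as a change. It is an error as written rather than a missing detail.

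The effect is possible, not shown. The number of patients affected is not given and may be zero. No effect in percentage points can be supported. It would need that number, and the Part 1 enrolment limits per indication are not in general the safety denominators, since SAP 2.1 reports Part 1 safety by dose level within tumor type with sub-groups merged.

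Two conclusions on direction hold. Excluding a patient who died early lowers the reported on-treatment death rate in that group. The direction for adverse event rates cannot be stated until the SAP says whether an adverse event or death record qualifies as an assessment.

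**What to change.** In the Safety set row of SAP Table 2-2, strike everything after PDR001 in "Patient who did not receive at least one dose of NIR178 or PDR001 or did not have at least one valid post-baseline safety assessment". Receipt of at least one dose is then the only criterion in that column, matching SAP 2.2.2 and Protocol 10.1.2.

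This is one wording change, made by the amendment or addendum route in SAP section 1. It needs no new data and carries no patient cost. If nobody is affected the results do not change; if somebody is, a treated patient is counted as both definitions require.
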